3.2 Research Content

3.2.1 Data Acquisition System

3.2.1.1 Molecular Feature Collection

(1) Sample Source: Obtain frozen tumor tissues ($\geq 3g$) from patients through surgical resection or tumor tissue samples obtained by puncture (puncture samples need to meet the pathological diagnosis requirements, and the sample quality can support subsequent transcriptome sequencing and analysis). Use the Illumina HiSeq platform for RNA - seq sequencing. The raw data undergoes quality control (FastQC), alignment (HISAT2), quantification (FeatureCounts), and differential expression analysis (DESeq2) to screen for differential genes with $FDR < 0.01$ and expression ratio > 4 . This part of the testing is outsourced to Hangzhou 迪安 Medical Laboratory Center Co., Ltd. for testing.

(2) Typing Algorithm: Perform hierarchical cluster analysis based on the 29 - gene set, and divide the subjects into a new typing cohort (unable to map to the TCGA HCC cluster) and other typing cohorts.

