Research plan

Study name

Study on the Identification of New Subtypes of Liver Cancer Based on 29 Genes and the Correlation with the Efficacy of Immunotherapy

Research Unit

Sir Run Run Shaw Hospital, Zhejiang University School of Medicine

Research Department

Department of General Surgery

Principal Investigator

[name]

Protocol Version Number

V1.0

Protocol Version Date

July 13, 2025

Study on the Identification of New Subtypes of Liver Cancer Based on 29 Genes and the Correlation with the Efficacy of Immunotherapy

I. Research Background

Liver cancer is one of the leading causes of cancer - related deaths worldwide. Its significant heterogeneity makes it difficult for traditional diagnosis and treatment models to meet the needs of individualized precision treatment. The application of immune checkpoint inhibitors (ICI) has brought breakthrough progress to liver cancer treatment, but there are still severe challenges in clinical practice. Although the dual - drug combination immunotherapy regimen has been widely used clinically, about 60% of patients will still experience primary or secondary drug resistance, resulting in significant differences in patients' treatment benefits.

There are two key bottlenecks in the current field that urgently need to be broken through, as follows:

(1) Lack of precise typing tools: The existing clinical and molecular typing systems cannot stably distinguish subtypes sensitive to immunotherapy, and it is difficult to provide reliable references for clinical decision - making, making it difficult to achieve precise application of immunotherapy;

(2) Lag in clinical translation process: Although a variety of immune checkpoint inhibitors have been clinically promoted and used, differentiated treatment strategies for different subtypes have not been established, and there is a lack of typing - guiding schemes verified by multiple centers.

To solve the above problems, this study intends to systematically develop a liver cancer typing system based on gene sets. The specific process is as follows: First, collect tumor and adjacent non - tumor tissue samples from patients with hepatocellular carcinoma, and perform whole - transcriptome sequencing to obtain transcriptome data; calculate the gene expression level of each patient sample based on the sequencing results, and then divide hepatocellular carcinoma into several subtypes through cluster analysis; map

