these subtypes to the TCGA HCC cluster respectively, and screen out the subtypes that cannot be completely matched as new subtypes; further analyze the differential genes between the new subtypes and other subtypes. The screening criteria are: the ratio of gene expression between the new subtype and other subtypes > 4 , the false discovery rate (FDR) < 0.01 , and the gene expression in the new subtype > 1 and < 1 in other subtypes. Through this method, this study finally obtained a set of differential genes containing 29 genes.

Based on this, this study plans to use this 29 - gene set as a standard, obtain frozen surgical tissues from liver cancer patients for transcriptome sequencing, type the patients, and compare the differences in immunotherapy response between the new subtype and other subtypes at the large - sample level, aiming to provide a basis for precise immunotherapy of liver cancer.

II. Research Objectives

Evaluate the differences in immunotherapy response (including indicators such as objective response rate, disease control rate, and progression - free survival) between the new subtype defined by the 29 - gene set system and other subtypes, and confirm that patients with the new subtype have a higher response rate to immunotherapy.

III. Research Design and Methods

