3.2.4 Protection Measures for Vulnerable Groups

The vulnerable groups that may be involved in this study include the mentally ill/cognitively impaired/critically ill patients/elderly/illiterate, etc. This study will take the following measures to protect their interests: 1) Ensure that the subjects are fully informed. If the subject is unable to read and sign the informed consent form due to

incapacity, their guardian shall act as the agent for the informed process and sign the informed consent form. If the subject is unable to read the informed consent form (such as illiterate subjects), a witness shall witness the informed process and sign the informed consent form. 2) If it is a critically ill patient, the researcher will closely monitor the vital signs of such subjects, and report in a timely manner once there is a situation.

IV. Sample Size Calculation

This study plans to include subjects from 10 top - three hospitals nationwide. Calculate the new typing score of HCC for each sample through the 29 - gene signature. It is estimated that there will be 100 cases in the new typing cohort and 250 cases in other typing cohorts.

Therefore, the final planned total sample size of this study is 350 cases.

V. Data Management and Confidentiality

All records related to the subject's identity will be kept confidential, and these materials will not be disclosed outside the scope permitted by relevant laws and/or regulations.

VI. Informed Consent

For the prospective observational study part involved in this study, before the subjects are included in this study, the researcher responsible for the informed consent discussion should introduce the purpose, nature, procedure, and possible benefits and risks of this study to them in written form completely and comprehensively. The subjects should be informed that they have the right to withdraw from the study at any time. Before inclusion, each subject should be fully informed and have sufficient time to consider whether to participate. Only after the subject voluntarily participates and signs the informed consent form can they be included in this study.

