For the retrospective study part involved in this study, if it only involves the use of previously saved clinical data and biological specimens, does not interfere with the clinical diagnosis and treatment process, and will not have an adverse impact on the health of the subjects. During statistical analysis, the identity of the subjects is represented by codes, and there is no disclosure of the subjects' privacy and personal information. This part of the study does not involve commercial interests and can apply for exemption from informed consent.

VII. Adverse Events and Related Handling Measures

For the prospective observational study part involved in this study, only clinical data of the subjects are collected, no additional biological samples are collected, and the clinical diagnosis and treatment process is not interfered with, which will not have an adverse impact on the health of the subjects.

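### Patients are typed by clustering the study subjects, with a per-sample 29-gene score left unlinked to it; a study meant to confirm a 29-gene standard should name one locked per-sample rule

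*Protocol*

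**What the plan says.** Section I describes discovery. Tumours were sequenced, and the plan was to "then divide hepatocellular carcinoma into several subtypes through cluster analysis". The clusters were compared with the TCGA classes in order to "screen out the subtypes that cannot be completely matched as new subtypes". Genes were then selected by criteria that include "the ratio of gene expression between the new subtype and other subtypes > 4", which left 29.

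For the present study, section I says "this study plans to use this 29 - gene set as a standard", and section II aims to "confirm that patients with the new subtype have a higher response rate to immunotherapy".

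Two places then describe how the 29 genes are used on study patients:

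- Section 3.2.1.1, item (2), the only text headed as the typing algorithm: "Perform hierarchical cluster analysis based on the 29 - gene set, and divide the subjects into a new typing cohort" and other cohorts. A parenthesis describes the new cohort as the one that cannot be mapped to TCGA.
- Section IV, Sample Size Calculation: "Calculate the new typing score of HCC for each sample through the 29 - gene signature". The estimate of 100 new-type and 250 other cases follows directly.

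Section VI allows for a retrospective part where "it only involves the use of previously saved clinical data and biological specimens".

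**The concern.** The label defines the two groups in the main comparisons: the log-rank and Cox analyses of TTP in section 3.2.3.2, and ORR and DCR in section 3.2.3.3.

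Hierarchical clustering suits discovery. As a typing rule for a predefined standard it has three weaknesses:

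- A patient near the boundary may be labelled differently according to which other samples are in the run.
- It yields no rule for the next single patient. A positive result would therefore not validate a test that another centre could apply, although section I gives the lack of precise typing tools as a reason for the study.
- A per-sample score on the same genes appears elsewhere, and nothing says which of the two decides the cohort. Where outcomes are already on file, that choice could be made after results are visible.

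Missing technical detail (linkage, cut height, score formula) is not the complaint; a SAP may supply it. The point is the method that the protocol names for a confirmatory purpose, and the second method beside it.

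**Working it through.** **1. The texts side by side.** Section 3.2.1.1 forms groups by clustering the subjects. Section IV computes one value per sample. Section I fixes the gene list but no classifier. TCGA mapping in section I is applied to whole subtypes; section 3.2.1.1 repeats the idea without a rule for one patient. The only related figure in the protocol, 100 + 250 = 350, adds up but does not bear on the choice of method.

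**2. Inputs for a size estimate.**

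- From the protocol: 350 patients, new-type share 100/350 = 28.6%, 29 genes, ratio above 4 (log2 4 = 2).
- Assumed, because the protocol gives no expression distribution: gene SD 1, 1.5 or 2 on the log2 scale; a shared per-sample effect of SD 0.7; log2 fold change either uniform on 2 to 4 (4- to 16-fold) or exactly 2 for all genes (worst case).
- Clustering: Ward. Either the highest-mean cluster is the new type (2 or 3 clusters), or each cluster takes the label of its nearest frozen discovery centroid (3 or 5 clusters), a rough stand-in for the TCGA anchor. TCGA data are not modelled.
- Frozen rules: the mean of the 29 genes cut at the midpoint of the class means in an independent discovery set of 200, or the nearest centroid from that set.

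**3. Results** (means over 200 to 300 simulated cohorts per setting; ranges run over gene SD).

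| Quantity | 4- to 16-fold | All at 4-fold |
|---|---|---|
| Clustering and frozen score disagree | 2.0-3.7% (7-13 of 350) | 7.9-11.2% (28-39 of 350) |
| Same, with the anchor stand-in | 1.6-3.3% (6-12) | 5.4-9.7% (19-34) |
| Same 175 patients change label when the other 175 are exchanged | 1.7-3.8% (3-7 of 175) | 6.7-14.1% (12-25 of 175) |
| Clustering error against true class | 1.8-3.9% | 9.3-14.6% |
| Frozen score error | 2.0-3.0% | 8.3-10.4% |
| Frozen centroid error | 1.7-2.6% | 8.3-10.4% |

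Under a frozen rule the third row is 0% by construction, provided normalisation is frozen too. That measures stability, not accuracy.

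**4. Closed-form check of the score error.** The score's within-class SD is s = √(0.7² + SD²/29), which is 0.724 at SD 1 and 0.792 at SD 2. With class difference D and a midpoint cut, error = Φ(−(D/2)/s).

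- D = 3 (the mean of 2 to 4): Φ(−1.5/0.724) = 1.9% and Φ(−1.5/0.792) = 2.9%.
- D = 2: Φ(−1/0.724) = 8.4% and Φ(−1/0.792) = 10.3%.

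These agree with the simulated 2.0-3.0% and 8.3-10.4%.

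**5. A different perturbation.** Dropping a random 70 of 350 patients and re-clustering at two clusters, with shifts of 0.5 to 3 SD per gene, changed a median 1-16% of the retained labels with Ward, 1-13% with average and 4-24% with complete linkage. At 3 SD it was 1-4%. For scale, a 4-fold difference is 2/2 = 1 SD when the gene SD is 2, and 2/1 = 2 SD when it is 1.

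**6. Calibration risk of a frozen cut-off.** Suppose study values sit δ above discovery values. Then error = (100/350)·Φ(−(D/2+δ)/s) + (250/350)·Φ(−(D/2−δ)/s). With δ = 0.5:

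- D = 3: 0.286 × 0.29% + 0.714 × 8.37% = 6.1% at SD 1; 0.286 × 0.58% + 0.714 × 10.35% = 7.6% at SD 2.
- D = 2: 0.286 × 1.92% + 0.714 × 24.5% = 18.0% at SD 1; 0.286 × 2.92% + 0.714 × 26.4% = 19.7% at SD 2.

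Two-cluster Ward is unaffected by a uniform shift (1.6-3.7% and 10.5-15.0% in the same model). Recentring without reference to outcome brings the score back to about 2-3% and 8-10% when discovery and study have the same subtype mix.

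**The case against.** The case for leaving the text alone has real weight.

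- **The score and the clusters may be compatible.** Section IV is a sample-size section and assigns nobody to a cohort. A reader might infer that the score decides membership and so contradicts section 3.2.1.1. The only support is its place just before the 100/250 estimate. The score could equally feed, summarise or check the clustering. No contradiction is shown; what stands is that the relation is unstated.
- **TCGA is an external anchor.** The protocol does not say that only enrolled subjects are clustered; the wording implies it. Clustering jointly with TCGA, or mapping to it, would lessen the dependence on the cohort. It would not remove it, and there is no per-patient mapping rule. The figures above do not measure the TCGA step.
- **No bias follows.** A reader might infer that the TTP and ORR comparisons are biased or the false-positive rate inflated. As described, the clustering uses expression and not response, so cohort dependence alone does neither.
- **A frozen rule is not plainly more accurate.** In the 4- to 16-fold setting the errors are almost equal, and an uncorrected calibration shift of 0.5 makes the frozen score worse. With 10 hospitals and both surgical and puncture samples, such a shift is conceivable. This stands, and it is why the rule must fix normalisation as well as a cut-off.
- **The study analyses one cohort.** Exchanging half the patients is not an event in this design. It only shows how far a label belongs to the patient rather than to the run, which matters because the aim is a standard for use beyond this cohort.

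**Conclusion.** The point holds as one of reproducibility and clarity. The protocol names a discovery method as the typing rule in a study meant to confirm a fixed gene standard, and places a per-sample score beside it without saying how they relate. Borderline labels then depend partly on the other samples clustered, no single new patient can be typed, and the choice between methods is open while retrospective outcomes may already exist.

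The size is modest and rests on assumed expression data: about 2-4% of labels if the genes are 4- to 16-fold, and roughly 7-14% if every gene sits at the 4-fold floor. The second is a worst case, since the selection rule requires a ratio above 4. The TCGA step could lower both. Nothing here supports a claim of biased TTP or ORR, of a material power loss, or of an outright contradiction between sections 3.2.1.1 and IV. It should be changed, with medium confidence: the text is clear, its numerical effect is not.

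**What to change.** Make sections 3.2.1.1 and IV state the same single per-sample rule: either the 29-gene score with a fixed cut-off, or assignment to the nearest frozen reference centroid. Fix the normalisation to the discovery or TCGA reference as part of the rule. Lock all of it before labels are linked to outcomes, including those of the retrospective part, and assign labels blind to response. Keep study-cohort clustering and TCGA mapping as a sensitivity analysis.

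Add an outcome-blind calibration check across sites and between surgical and puncture samples, with recentring specified in advance. Recentring assumes a similar subtype mix in the discovery and study samples, so that assumption should be stated.

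Cost: a short amendment, the same RNA-seq and no added patients. Downsides: a frozen cut-off is sensitive to calibration shifts, borderline patients are labelled by rule, the new-type count may differ from 100, and labelling error falls little if the genes are well above 4-fold.

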3.2.1.2 Clinical Data Integration

Structured extraction of subjects' baseline data (age, gender, Child - Pugh class, etc.), treatment information (targeted - immunotherapy combination regimen, dosage, and cycle, etc.), imaging evaluation (enhanced CT/MRI reports, etc.), and survival status (last follow - up date or death time, etc.) from the electronic medical record system. Simultaneously collect AFP (electrochemiluminescence method), PIVKA - II (enzyme - linked immunosorbent assay), and liver function biochemical data (total bilirubin, albumin, INR, etc.). The detection frequency matches the imaging evaluation cycle (that is, equivalent to clinical routine).

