3.1.1 Inclusion Criteria

- ① ≥ 18 years old.
- ② Patients who are treated in multiple centers including Sir Run Run Shaw Hospital, Zhejiang University School of Medicine (the leading unit) and diagnosed with primary hepatocellular carcinoma by surgical pathological histology.
- ③ They have received targeted drug combined with immune checkpoint inhibitor treatment after the specimen collection time point (post - surgery or post - puncture) (that is: local treatments such as TACE, ablation, etc. are allowed before the start of targeted - immunotherapy combination treatment, but an interval of ≥ 4 weeks from the targeted - immunotherapy treatment is required).
- ④ Have measurable tumor lesions at the observation start point (according to RECIST 1.1 criteria), and can judge the tumor response status (including complete response CR, partial response PR, stable disease SD, or progressive disease PD) through imaging examination during the observation (such as post - treatment evaluation).
- ⑤ Have accessible frozen tumor tissue samples from surgical resection (sample volume $\geq 3g$); or tumor tissue samples obtained by puncture (puncture samples need to meet the pathological diagnosis requirements, and the sample quality can support subsequent transcriptome sequencing and analysis).
- ⑥ Voluntarily participate in this study and sign the informed consent form. If the subject

is unable to read and sign the informed consent form due to incapacity and other reasons, their guardian shall act as the agent for the informed process and sign the informed consent form. If the subject is unable to read the informed consent form (such as illiterate subjects), a witness shall witness the informed process and sign the informed consent form.

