3.2.2 Immunotherapy Response Evaluation System

3.2.2.1 Primary Observation Indicators

(1) Time to Progression (TTP)

Definition: The time from the start of targeted - immunotherapy combination treatment to

the first time meeting the mRECIST progression criteria.

Evaluation Criteria:

Target lesions: The sum of the diameters of arterial - phase enhancement increases by $\geq 20\%$ compared to the baseline and the absolute value $\geq 5\text{mm}$;

Non - target lesions: New lesions appear or existing non - target lesions have definite progression;

Distant metastasis: New occurrences of lung, bone, or lymph node metastases.

(2) Objective Response Rate (ORR)

Definition: The proportion of patients achieving complete response (CR, disappearance of arterial - phase enhancement in all target lesions) and partial response (PR, the sum of the diameters of target lesions is reduced by $\geq 30\%$).

Evaluation Time: For each line of targeted - immunotherapy combination treatment regimen received by the patient, the determination is made simultaneously at Week 8, Week 16, Week 24 of the regimen treatment, and at disease progression (or regimen termination). If the patient changes the targeted - immunotherapy treatment regimen due to poor efficacy, the treatment cycle of the new regimen needs to be recorded separately (Weeks 8, 16, 24 are recalculated from the start time of the new regimen), and the CR/PR status is evaluated at the corresponding time points. In the final ORR calculation, the CR/PR status achieved by the patient in a certain regimen only corresponds to the treatment cycle and evaluation time of that regimen, that is, it is clearly associated with the efficacy data of the specific targeted - immunotherapy combination regimen (including the first regimen or the subsequent new regimens).

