3.2.3.2 Survival Analysis

Use the Kaplan - Meier method to draw survival curves of time to progression (TTP) and post - progression survival (PPS), and compare the survival differences between the new typing cohort and other typing cohorts through Log - rank test; use the Cox proportional hazards regression model to analyze the impact of 29 - gene set typing and clinical factors (such as Child - Pugh class, changes in tumor markers) on the progression risk.

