3.2.3.3 Immunotherapy Response Analysis

The differences between groups in objective response rate (ORR) and disease control rate (DCR) are verified by chi - square test or Fisher's exact probability method, and the efficacy judgment follows the mRECIST criteria.

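### Both primary subtype comparisons are unadjusted for treatment received, although any targeted drug plus checkpoint inhibitor qualifies and regimen is already collected

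*Protocol*

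**What the plan says.** **Who enters.** The only treatment requirement in 3.1.1 is criterion 3: "They have received targeted drug combined with immune checkpoint inhibitor treatment after the specimen collection time point". It names no agent, class or line. The exclusions in 3.1.2 deal with local treatment and, in item 9, with other antineoplastic drugs given at the same time. None excludes earlier systemic treatment.

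**What is recorded.** Section 3.2.1.2 extracts "treatment information (targeted - immunotherapy combination regimen, dosage, and cycle, etc". Section 3.2.2.1 has ORR assessed "For each line of targeted - immunotherapy combination treatment regimen received by the patient" and adds that "the CR/PR status achieved by the patient in a certain regimen only corresponds to the treatment cycle and evaluation time of that regimen".

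**What is tested.** Section 3.2.2.1 makes TTP and ORR the primary indicators. Under 3.2.3.3, group differences in ORR "are verified by chi - square test or Fisher's exact probability method". For TTP, 3.2.3.2 will "compare the survival differences between the new typing cohort and other typing cohorts through Log - rank test". A Cox model then covers typing and "clinical factors (such as Child - Pugh class, changes in tumor markers) on the progression risk".

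**Where treatment enters an analysis.** Section 3.2.2.2 takes differences in treatment plan into account for post-progression survival, a secondary indicator. No analysis of a primary indicator is described in that way.

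**The concern.** Section II aims to confirm that the new subtype responds better to immunotherapy. Subtype cannot be randomised, treatment is routine care at 10 hospitals, and the protocol sets no common regimen. A chi-square or log-rank test on the whole cohort therefore compares subtype together with whatever treatment each subtype happened to receive.

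Two conditions must both hold for this to bias the result: regimen or line must be distributed differently across the subtypes, and it must affect response or progression. If both hold, part of the observed difference belongs to treatment. This could create an apparent advantage for the new subtype, or hide a real one.

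This goes beyond detail left to a SAP. The protocol names the tests for both primary indicators, and the named tests take no account of treatment.

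**Working it through.** **The plan's own figure.** Section IV gives 100 + 250 = 350, which adds up. It gives no response rate, effect size or power, so the size of any bias cannot be derived from the protocol. What follows is an illustration on assumed rates.

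**Inputs**
- From the protocol: n1 = 100 (new subtype), n2 = 250 (others), P < 0.05 (3.2.3.4). Two-sided testing is assumed, because the protocol does not state it.
- Assumed: two regimen classes, A and B, with ORRs a and b that are the same in both subtypes, so there is no subtype effect. Class A is used by a share s1 of the new subtype and s2 of the others.

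**Formulas**
- p1 = s1·a + (1 − s1)·b and p2 = s2·a + (1 − s2)·b
- Spurious difference: d = p1 − p2 = (s1 − s2)(a − b)
- Pooled rate: p̄ = (100·p1 + 250·p2)/350
- SE0 = √[p̄(1 − p̄)(1/100 + 1/250)] and SE1 = √[p1(1 − p1)/100 + p2(1 − p2)/250]
- Rejection rate = Φ[(d − 1.96·SE0)/SE1] + Φ[(−d − 1.96·SE0)/SE1]

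**One case in full** (a = 40%, b = 20%, s1 = 70%, s2 = 40%)
- p1 = 0.7×0.40 + 0.3×0.20 = 0.34; p2 = 0.4×0.40 + 0.6×0.20 = 0.28; d = 0.06
- p̄ = (34 + 70)/350 = 0.297; SE0 = √(0.297×0.703×0.014) = 0.0541
- SE1 = √(0.34×0.66/100 + 0.28×0.72/250) = 0.0552
- Rejection = Φ[(0.06 − 0.106)/0.0552] + Φ[(−0.06 − 0.106)/0.0552] ≈ 0.203 + 0.001 = 20.4%

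**All cases**

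| ORR of A / B | Use of A, new vs others | Spurious difference | Rejection rate |
|---|---|---|---|
| 40% / 20% | 60% vs 40% | 4 points | about 12% |
| 40% / 20% | 70% vs 40% | 6 points | about 20% |
| 35% / 25% | 60% vs 40% | 2 points | about 7% |
| 35% / 25% | 70% vs 40% | 3 points | about 9% |
| any | equal | 0 | 5% |

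Simulation (200,000 runs per case) agrees with these values. A Mantel-Haenszel test stratified by regimen rejects in about 5% of runs in every case.

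**Direction.** If the shares are reversed, so that the new subtype receives the more active class less often, the spurious difference changes sign. It is −4 and −6 points in the first two rows and −2 and −3 in the next two.

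**Scale.** By the usual two-proportion power formula, 100 vs 250 has about 80% power for an ORR difference of 15 to 16 points (20% vs 35%: 82.5%; 30% vs 46%: 80.6%). Spurious differences of 2 to 6 points are smaller than that, but they are not negligible.

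**The case against.** **Covariates belong in a SAP.** The Cox list is open: it gives "clinical factors (such as Child - Pugh class, changes in tumor markers") as examples, and regimen could be added. This stands for the Cox model, and it would be wrong to infer that the protocol rules out adjusting TTP for treatment. It does not extend to the log-rank test or to ORR, for which no adjusted analysis is described.

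**Treatment data are used.** A reader might infer that the plan ignores regimen altogether. It does not: 3.2.2.1 attaches each response to its regimen, and 3.2.2.2 considers treatment plans for survival after progression. Neither step stratifies or adjusts the primary subtype comparison.

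**The bias is conjectural.** A reader might infer that any uneven spread of regimens raises the false-positive rate, or that the bias must favour the new subtype. Neither follows. Regimens or lines must also differ in effect, and the bias can run either way. The documents do not say how physicians choose regimens, or whether regimens vary within a hospital. The 20% figure needs both a 30-point imbalance in use and a 20-point gap in efficacy; the milder cases give 7% to 9%.

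**Adjustment can take away too much.** Subtype is read from tissue taken before the treatment under study. If line of treatment is partly a consequence of subtype, adjusting for it may absorb real subtype effect. This stands, and it is why both results should be shown.

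**Conclusion.** The point holds in a limited form. For a non-randomised comparison with open treatment eligibility, the protocol fixes unadjusted tests for both primary indicators and does not carry the regimen data it collects into them. The direction and size of any bias are unknown. Under the assumed rates above it is 2 to 6 ORR points, with a rejection rate of about 7% to 20% instead of 5%; with equal regimen use or equal regimen efficacy it is nil. The TTP comparison is open to the same mechanism, but its size was not calculated. The documents do not show that an imbalance exists. They show only that the stated tests would not deal with one. This should be corrected, and the correction is inexpensive.

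**What to change.** **Change**
- In 3.2.3.3, make the main ORR comparison a Cochran-Mantel-Haenszel test or a logistic model.
- In 3.2.3.2, make the main TTP comparison a stratified log-rank test or a Cox model.
- Adjust both for starting regimen class, grouped in advance into two or three classes, and, where the medical record shows it, for line of systemic treatment at the start.
- Do not adjust for later dose changes or number of cycles, because these follow from response and toxicity.
- Report the unadjusted tests alongside.

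**Cost**
- Regimen is already extracted. Earlier systemic treatment is not a listed item in 3.2.1.2, so line may need one further field from the same medical record.
- Intervals will be slightly wider, and more so if strata are small, hence the limit of two or three classes.
- If line is itself a consequence of subtype, the adjusted estimate may understate the subtype effect; the unadjusted result lets the reader see this.

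No change to anyone's treatment is involved.
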